### 6.2.2 *SCORing Atopic Dermatitis (SCORAD)*

To determine disease severity the SCORing Atopic Dermatitis (SCORAD) index uses the rule of nines to assess disease extent (head and neck 9%; upper limbs 9% each; lower limbs 18% each; anterior trunk 18%; back 18%; genitals 1%; and hands 2%) and evaluates six clinical characteristics – erythema, edema/papulation, oozing/crusts, excoriation, lichenification and dryness – each on a scale of 0 to 3 (0 = none, absent; 1 = mild; 2 = moderate; 3 = severe). SCORAD also assesses subjective symptoms of pruritus and sleep loss with visual analogue scales (VAS) where 0 is no itch (or no sleeplessness) and 10 is the worst imaginable itch (or sleeplessness). These three aspects: extent of disease (A: range 0-102), disease severity (B; range 0-18) and subjective symptoms (C: range 0-20) will be combined using,  $A/5 + 7*B/2 + C$ , to give a maximum possible score of 103.4.

The SCORAD will be assessed at baseline and at Weeks 1, 4, 8, 12, and 16 post-randomization, plus at the early termination visit, if applicable. At each of the post-baseline visits the SCORAD will be computed, and the SCORAD score will be compared with the SCORAD score obtained at baseline to obtain change and percent change from baseline. Descriptive statistics for the SCORAD value and the subjective assessments of pruritus and sleep loss and the respective changes from baseline will be tabulated for each time point using the overall and by-country populations.

The MMRM and ANCOVA analyses described in [Section 6.2.1](#) will be performed to compare the baricitinib treatment arms and placebo for change and percent change from baseline in the SCORAD score, and change from baseline in the pruritus and insomnia assessments. The tabular outputs for the MMRM and ANCOVA analyses described will be provided.

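### The SCORAD extent weights in SAP Section 6.2.2 total 102% of body surface, so the stated range of A (0-102) and maximum score (103.4) exceed what a body-surface percentage allows

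*SAP*

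**What the plan says.** Section 6.2.2 of the SAP states that the index "uses the rule of nines to assess disease extent" and lists the regional percentages as "head and neck 9%; upper limbs 9% each; lower limbs 18% each; anterior trunk 18%; back 18%; genitals 1%; and hands 2" (the last figure is also a percentage). It then gives the ranges of the three components: "extent of disease (A: range 0-102"), "disease severity (B; range 0-18") and "subjective symptoms (C: range 0-20"). The components are combined as A/5 + 7B/2 + C, "to give a maximum possible score of 103.4".

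SCORAD is a secondary endpoint in Table JAHG.1 (Section 1.2), assessed at Weeks 1, 4, 8, 12 and 16. Section 6.2.2 applies the MMRM and ANCOVA models of Section 6.2.1 "to compare the baricitinib treatment arms and placebo for change and percent change from baseline in the SCORAD score".

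The section does not say whether the upper limbs include or exclude the hands. It sets no cap on A, and it gives no reason for a scale that runs to 102.

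**The concern.** A is built by adding percentages of body surface. Such a sum describes a share of the whole body and cannot pass 100. Here it can reach 102, and both the stated range and the stated maximum accept that. A programmer who follows the section would write a derivation and range checks that allow more than the whole skin to be affected.

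The excess is not a constant offset. It depends on how much of the hands or arms is involved, so it need not cancel when a follow-up score is compared with baseline. What is at stake is the correct definition of a secondary endpoint. The primary EASI-50 analysis, the sample size and the control of the type 1 error do not depend on it.

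**Working it through.** **Inputs**, all from SAP Section 6.2.2: head and neck 9; upper limbs 9 each; lower limbs 18 each; anterior trunk 18; back 18; genitals 1; hands 2; six signs scored 0 to 3; two visual analogue scales scored 0 to 10; score = A/5 + 7B/2 + C.

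**Step 1: reproduce the plan's figures.**
- A maximum = 9 + 2×9 + 2×18 + 18 + 18 + 1 + 2 = 102
- B maximum = 6×3 = 18
- C maximum = 2×10 = 20
- Score maximum = 102/5 + 7×18/2 + 20 = 20.4 + 63 + 20 = 103.4

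All four agree with the SAP.

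**Step 2: locate the excess.**
- Without hands: 9 + 18 + 36 + 18 + 18 + 1 = 100
- Excess = 102 − 100 = 2, which equals the hands entry

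**Step 3: take both readings of upper limbs.**
- Hands included in the 9% per arm: affected hand skin enters A once through the arm and again through the hands entry. With both hands fully affected it contributes 2 + 2 = 4 to A instead of 2, an excess of 2.
- Hands excluded from the 9% per arm: no lesion is counted twice, but arms and hands together carry 18 + 2 = 20 where the other regions leave only 100 − 82 = 18. Taking the hands' 2% out of the arms gives 8 per arm, so 9 is too large by 1 on each side, again an excess of up to 2.

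**Step 4: size on the score scale.**
- Largest excess = 2/5 = 0.4 points on either reading
- As a share of the stated maximum: 0.4/103.4 = 0.39%

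**Step 5: corrected range.**
- Hands within the upper-limb 9%: 9 + 18 + 36 + 18 + 18 + 1 = 100
- Upper limbs 8% each plus hands 2%: 9 + 16 + 36 + 18 + 18 + 1 + 2 = 100
- Maximum score either way = 100/5 + 63 + 20 = 103.0

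**Step 6: effect on percent change (assumed scores, for illustration only).** Suppose the score without the excess falls from 60 to 30, a reduction of 50.0%.
- Full excess at baseline, none at follow-up: (60.4 − 30)/60.4 = 50.3%
- Full excess at both visits: (60.4 − 30.4)/60.4 = 49.7%

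**Comparison within the SAP.** The other area-weighted score, EASI in Section 6.1, uses multipliers 0.2 + 0.2 + 0.3 + 0.3 = 1.0, with no excess.

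**The case against.** The strongest reply is that nothing has been added up wrongly. The list, the range of A and the maximum agree with one another, which suggests that the authors knew the scale ran to 102. SCORAD is a named index rather than the sponsor's own design, and Section 1.1 of the SAP sends readers to the protocol and eCRF for procedures and collected variables. The form in use may tell raters how to treat the hands. On this view a score is too high only against a reference that the SAP does not show.

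Part of this stands. The section does not contradict itself, and it would be wrong to call this a summation slip. What the published instrument or the study form prescribes cannot be checked from the SAP. But agreement among the three figures shows only that the excess was carried through. It does not give 102% of a body surface a meaning under a method that the section itself calls the rule of nines.

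A reader might infer that hand eczema is counted twice in every patient with affected hands, so that all their scores are too high and their changes materially distorted. The SAP does not support that. Double counting follows only if the upper limbs include the hands, and the text is silent on this. Under the other reading the excess lies in the arm weights. The size is also slight: the full 0.4 points arises only when the hands (first reading) or the arms (second reading) are wholly affected, the same rule applies in all arms and at all visits, and Section 6.2.2 sets no SCORAD responder threshold that could reclassify a patient.

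**Conclusion.** The point holds as a minor error in a scoring definition. The weights total 102%, and the range 0-102 and the maximum 103.4 are therefore wrong for a sum of body-surface percentages, whichever way the upper limbs are read. The total of 102 is plain from the text; double counting of the hands is one of two possible explanations.

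The largest effect is 0.4 points per assessment on a secondary endpoint, and it is not expected to change any treatment conclusion. This rests on two assumptions: that A is meant as a percentage of body surface, as the named method implies, and that the weights are applied as listed.

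**What to change.** Check the regional list against the SCORAD scoring form and the eCRF, and state in Section 6.2.2 whether the upper limbs include the hands. Then make the weights sum to 100 by counting hand skin once, in whichever of these ways matches the form:

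- hands within the upper-limb 9%, with no separate hands entry in A; or
- upper limbs 8% each plus hands 2%.

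State A as 0-100 and the maximum as 103.0. If the form itself proves to use a 102 scale, the SAP should say so and give the basis, so that it does not depart from the form without notice.

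Do not rely on capping A at 100. A cap acts only on patients with nearly all of their skin affected and leaves any double count in place for everyone with A below 100. Once the weights sum to 100 it is redundant.

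The cost is one line in the SAP and one in the derivation program, best settled before the score is derived. The only downside is that some scores will be up to 0.4 points lower than under the listed weights.

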### ***6.2.3 Investigator's Global Assessment***

The Investigator's Global Assessment (IGA) uses the clinical characteristics – erythema, infiltration, papulation, oozing and crusting – as guidelines for the overall severity assessment. The IGA consists of a 6-point severity scale from clear to very severe disease (0 = clear, 1 = almost clear, 2 = mild disease, 3 = moderate disease, 4 = severe disease and 5 = very severe disease).

The IGA will be assessed at baseline and at Weeks 1, 4, 8, 12, and 16 post-randomization, plus at the early termination visit, if applicable. At each of the post-baseline visits the IGA will be computed, and the IGA score will be compared with the IGA score obtained at baseline to obtain change from baseline. Descriptive statistics for the value and change from baseline will be tabulated for each time point using the overall and by-country populations.

An IGA [0,1] responder is defined as a patient with a post-baseline score of 0 (clear) or 1 (almost clear), and an IGA [0,1] responder with a 2-point drop is a responder whose change from baseline is at least 2 points. An IGA [0] responder is defined as a patient with a post-baseline score of 0 (clear). At each post-baseline time point and the last observation the number and percent of IGA [0,1] responders both overall and those with at least a 2-point drop from baseline will be compared between each baricitinib arm and placebo using a two-sided Fisher's Exact test at level  $\alpha = 0.05$ . A similar analysis will be performed for IGA [0].

In addition, a bar chart that shows the percentage of IGA [0,1] responders with a 2-point drop in each treatment arm and at each time point including the patient's last assessment will be presented. The figure will be generated for the overall population and by country.

Analyses will also be performed for change from baseline at each post-baseline time point and for the last observation. Comparisons between each baricitinib arm with placebo will be based on chi-square statistics using the row mean scores option. The number and percentage of patients having change from baseline scores (range: -5 to 5) will be tabulated for each treatment arm and each time point. The associated p-values at each time point will also be presented for each pairwise comparison.

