
 
• To evaluate the mean change from baseline compared to placebo for the SCORing Atopic Dermatitis (SCORAD)
 
• To evaluate the mean change from baseline compared to placebo for the Investigator’s Global Assessment (IGA)
 
• To assess quality of life based on the Dermatologic Life Quality Index (DLQI)
 
• To assess itch based on the Itch Numerical Rating Scale (NRS)
 
• To characterize the pharmacokinetics of baricitinib in patients with moderate-to-severe atopic dermatitis
 
 
Exploratory
 
 
• To evaluate EASI response in patients based on their baseline total serum IgE
 
• To evaluate total serum IgE over the course of treatment
 
 
Exploratory (continued)
 
 
• To evaluate changes in disease activity over the course of treatment
 
• To evaluate changes in sleep quality over the course of treatment
 
• To evaluate changes in nocturnal itch patterns over the course of treatment
 
• To evaluate EASI response relative to filaggrin genotype
 
• To assess tissue biomarkers from biopsies
 
• To assess peripheral biomarkers mechanistically related to inhibition of JAK 1/2 mechanism
 
	
 
• SCORAD at Weeks 1, 4, 8, 12, and 16
 
• IGA at Weeks 1, 4, 8, 12, and 16
 
• DLQI at Weeks 1, 4, 8, 12, and 16
 
• Itch Numerical Rating Scale at Weeks 1, 4, 8, 12, and 16
 
• Plasma pharmacokinetic data
 
• EASI at Weeks 1, 4, 8, 12 and 16; baseline total serum IgE
 
• Total serum IgE at baseline, Weeks 4, and 16
 
• Patient-Oriented Eczema Measure (POEM) at Weeks 1, 4, 8, 12, and 16
 
• Change from baseline with data from a wearable actigraphy device
 
• Change from baseline with data from a wearable actigraphy device
 
• EASI-50 and filaggrin genotype data from peripheral baseline blood sample
 
• K16, Ki-67, and IL-4 will be assessed from each tissue biopsy (collected at baseline (lesion and non-lesion), at Week 4 (lesion), and at Week 16 (lesion and non-lesion))
 
• Peripheral biomarkers collected at baseline, Weeks 4 and 16
 

--	---

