## 2.4 Adjustment for Multiple Centers

The study randomization is stratified by country of the investigative site, and only investigative centers from Japan and the United States are included in the study. The number of patients to be randomized in each country is not fixed, so there may be low enrollment in one of the countries. The stratification variable “country” will not be included in the statistical model by default. If there are at least 15 patients enrolled in each country, analyses that include a fixed effect for country may be performed as exploratory analyses.

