## 6.2 Secondary Efficacy Analyses

### 6.2.1 *Change and Percentage Change in EASI*

Change and percentage change from baseline for EASI will be derived for each patient at each post-baseline visit (Weeks 1, 4, 8, 12, and 16). Descriptive statistics for the value, change and percentage change will be tabulated for each time point.

Missing assessments will assumed to be missing at random and separate mixed effects model repeated measures (MMRM) analyses will be performed to compare the baricitinib treatment arms and placebo for the actual and percent change from baseline. For both change and percent change from baseline the MMRM model will contain fixed effects for treatment, visit, and country and the treatment-by-visit interaction plus the baseline value and baseline-by-visit term as covariates. Patient will be nested within treatment, and the covariance structure among the repeated measurements for a patient will be assumed to be common across patients and modeled using an unstructured 5x5 matrix. Satterthwaite's approximation will be used to estimate denominator degrees of freedom. The significance of differences in least-square means will be based on Type III tests using the observed population margins. The analyses will be performed using the SAS procedure PROC MIXED.

The tabular output for these MMRM analyses will present the least squares means, standard errors and 95% confidence intervals and p-values for each main effect marginal. Pairwise contrasts of the least squares means between the randomized treatment arms will also be provided at each time point using LSMESTIMATE statements.

For both endpoints plots of the least squares mean  $\pm$  standard error estimates for changes in EASI over time will be provided by randomized treatment. These plots will be provided for the overall population and for each country.

Finally, a last observation analysis will be performed for both change and percent change using an analysis of covariance (ANCOVA) model with fixed effects for treatment and country plus the baseline value as a covariate. Tabular output for these ANCOVA analyses will present the least squares means, standard errors and 90% confidence intervals and p-values for each main effect marginal. Pairwise contrasts of the least squares means will also be provided for randomized treatment arms at each time point.

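### Stratifying the IGA change test in SAP Section 6.2.3 by baseline IGA would be a cheap gain in precision; the planned test is valid but makes no such adjustment

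*SAP*

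**What the plan says.** Table JAHG.1 lists a secondary objective on mean IGA change versus placebo, with the endpoint "IGA at Weeks 1, 4, 8, 12, and 16".

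Section 6.2.3 describes the instrument: "The IGA consists of a 6-point severity scale from clear to very severe disease". On the analysis it says "Analyses will also be performed for change from baseline at each post-baseline time point and for the last observation", and then "Comparisons between each baricitinib arm with placebo will be based on chi-square statistics using the row mean scores option". No stratification factor or covariate is named, and the section contains no MMRM or ANCOVA for IGA.

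Section 6.2.1 analyses change in EASI by an MMRM with country, baseline and baseline-by-visit terms, and by an ANCOVA with "fixed effects for treatment and country plus the baseline value as a covariate". Sections 6.2.2, 6.2.4 and 6.2.5 apply these models to SCORAD, DLQI and Itch NRS.

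On country, Section 2.4 states "The study randomization is stratified by country of the investigative site", but adds that this variable "will not be included in the statistical model by default". It continues: "If there are at least 15 patients enrolled in each country, analyses that include a fixed effect for country may be performed as exploratory analyses".

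**The concern.** Among the secondary efficacy scales, only IGA has a change analysis without baseline adjustment, and the SAP gives no reason specific to IGA. Section 2 allows a nonparametric method as first choice. That explains the row mean scores test but not the absence of strata, because the same statistic can be stratified and remain nonparametric.

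Subtracting baseline is not the same as adjusting for it. The scale is bounded: a patient who starts at 3 can fall by at most 3 points, one who starts at 5 by up to 5. If follow-up IGA depends only weakly on baseline, patients with a high baseline show larger falls in every arm. That spread adds noise to the comparison, and a chance difference in baseline IGA between arms of about 48 and 36 passes into it. At stake is power, and robustness to chance imbalance, for one secondary endpoint.

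**Working it through.** **The plan's own figure.** The SAP has one power statement, for EASI-50: 90% for a 35-point difference, two-sided alpha 0.05, N = 120 at 4:3:3. That allocation gives 48:36:36. No placebo rate is stated. Taking 30% versus 65% on all randomised patients:

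- pooled rate = (48×0.30 + 36×0.65)/84 = 0.45
- null SE = √[0.45×0.55×(1/48 + 1/36)] = 0.1097
- alternative SE = √[0.30×0.70/48 + 0.65×0.35/36] = 0.1034
- z = (0.35 − 1.96×0.1097)/0.1034 = 1.31, so power is 90.4%

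The result is 90.4% to 91.1% for placebo rates of 25% to 40%, so the stated figure reproduces. It says nothing about IGA, for which the SAP gives no effect, SD or correlation.

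**Formula.** Let r be the correlation of baseline with follow-up, and k the baseline SD divided by the follow-up SD. A change score fixes the baseline slope at 1, whereas the least-squares slope is r/k. The change score over-corrects when r < k, and a fraction 1 − r/k of any baseline imbalance carries into the comparison. The variance of the adjusted estimate relative to the change-score estimate is

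(1 − r²)/(1 + k² − 2rk).

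| r | k = 0.6 | k = 1.0 |
|---|---|---|
| 0 | 1/1.36 = 0.74 | 1/2 = 0.50 |
| 0.2 | 0.96/1.12 = 0.86 | 0.96/1.6 = 0.60 |
| 0.4 | 0.84/0.88 = 0.95 | 0.84/1.2 = 0.70 |
| 0.6 | 0.64/0.64 = 1.00 | 0.64/0.8 = 0.80 |

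At k = 0.6, adjustment saves between 26% of the variance and nothing. If the SDs are equal, it saves 50% to 20%.

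**Simulation.** There were 2,000 trials per setting, 38 versus 29 patients. These are the 96 completers of Section 1.3 split 4:3:3 (38.4 and 28.8, rounded). The IGA inputs are all assumptions: baseline 3/4/5 in 50/40/10% of patients, latent follow-up SD 1.05, latent treatment shift 0.75, 30% of patients in one country, and a country effect of 0 or 0.5. The statistic is

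Q = [Σₛ(Tₛ − aₛȳₛ)]² / Σₛ[aₛ(nₛ − aₛ)/nₛ × Sₛ²],

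referred to 3.841. In stratum s, Tₛ is the summed change in the baricitinib arm, aₛ that arm's size, nₛ the stratum size, and ȳₛ and Sₛ² the mean and variance of change. The planned test uses a single stratum.

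Power with no country effect:

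| Latent r | Planned | Strata: baseline IGA | Strata: baseline × country, unpooled |
|---|---|---|---|
| 0 | 64.7% | 76.8% (+12.1) | 74.9% (+10.2) |
| 0.2 | 72.1% | 77.6% (+5.5) | 75.4% (+3.3) |
| 0.4 | 81.5% | 83.0% (+1.5) | 81.2% (−0.3) |
| 0.6 | 93.4% | 92.3% (−1.1) | 91.2% (−2.2) |

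With a country effect of 0.5, baseline strata changed power by +11.0, +5.7, +1.6 and −0.7 points. Country strata alone moved power by about −1 to +2 points in all settings. With no treatment effect, rejection rates were 4.2% to 5.5% for every version, including the planned one. Runs at 48 versus 36 showed the same pattern, and pooling baseline to 3 or less versus 4 or more kept most of the gain.

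**The case against.** The strongest reply is that nothing here is wrong. The planned test is valid, suits a six-point ordinal scale, needs no normality assumption and requires no pooling rule. The SAP uses row mean scores without named strata elsewhere, for POEM bands and QIDS-SR16 levels, and its primary EASI-50 test is an unadjusted chi-square. Omitting country follows the default in Section 2.4, which is motivated by possibly low enrolment in one country. The size of the loss depends on quantities that the SAP does not give, and it may be nil.

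Most of this stands. A reader might infer that the test ignores baseline IGA; it does not, since change is the variable tested. A reader might also infer that the test is invalid, or that leaving out country breaks the plan. The type I error results rule out the first, and Section 2.4 the second. If anything conflicts with Section 2.4, it is Section 6.2.1, which puts country into its models. That the test is unstratified is itself read from silence, although the Section 2.4 default supports that reading for country.

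The reply does not supply a reason for omitting baseline strata. A stratified row mean scores test keeps the stated advantages apart from the freedom from a pooling rule. Ordinality does not separate IGA from Itch NRS, a single 11-point item that is modelled with baseline. POEM, although exploratory, also gets adjusted change models besides its banded comparison.

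**Conclusion.** This is a cheap improvement, not a correction of an error. Section 6.2.3 makes no adjustment for baseline IGA beyond subtraction, unlike the change analyses of the other secondary scales. Under the assumed inputs, baseline strata would gain about 12 power points at correlation 0 and about 6 at 0.2. The gain is 1 to 2 points at 0.4 and none at 0.6, where about one point is lost. Nearly all of it comes from baseline IGA; country contributes little.

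The 12-point figure should not be read as the expected loss: it belongs to zero correlation, the most favourable setting examined. Nor can the planned analysis be said to have no benefit. That criticism fits only the omission of strata, not the choice of test.

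**What to change.** In Section 6.2.3, keep the row mean scores statistic and stratify it by baseline IGA category. State the pooling rule for sparse strata before unblinding, for example 3 or less versus 4 or more.

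Also stratify by country when each country has enough patients; the threshold of 15 in Section 2.4 could serve. This would match the stratified randomisation and the Section 6.2.1 models, but should not be expected to add power. It requires Section 2.4 to be reconciled with Section 6.2.1 and with the new text, since Section 2.4 leaves country out by default and treats country models as exploratory.

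The cost is one or two stratification variables in the same procedure, plus the pooling rule. The statistical downside at high correlation is about one power point with baseline strata alone. It was about two points with baseline and country fully crossed, which is a reason to pool.

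A stratified test still yields only a p-value. If an adjusted mean difference with an interval is wanted for the mean-change objective, the Section 6.2.1 ANCOVA could be added for IGA as a supporting analysis.
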